    - If  $6 \le$  number cancellation item score  $\le 11$  then re-scale as 4
    - If  $0 \le \text{number cancellation item score} \le 5 \text{ then re-scale as } 5$ 
      - Number cancellation item scores < 0 will be re-scaled as 5
  - The resulting final number cancellation item score will range from 0 to 5.
- The ADAS-13 total score will be derived as the sum of the 13 individual items, but using the score for the number cancellation item which has been re-derived as described above.
- The ADAS-11 total score is the sum of 11 individual items excluding delayed recall and number cancellation.
- The Cognitive Composite score will be calculated using z-scores of the below items. The z-scores will be derived by calculating the baseline mean and standard deviation of each individual component for all participants. A z-score within each component will be derived for each participant at each timepoint by subtracting the corresponding baseline mean and then dividing by the corresponding baseline SD. The Cognitive Composite score will be set as the mean of the 10 individual z-scores (5 ADAS-COG scores and 5 NTB scores) within each participant and timepoint. If a participant is missing one, two, or three scores at a particular timepoint, the missing scores will be set as the average non-missing z-score of all participants at that timepoint within each component when deriving the Cognitive Composite score. If a participant is missing four or more individual components at each timepoint, the Cognitive Composite score will not be derived.
  - o ADAS-COG
    - Word recall (scored on a 0 to 10 range), average of trials I, II, and III. If at least one of the trials is missing, this component will be considered missing. The sign of the z-score for this component will be reversed when deriving the Cognitive Composite score as it is the total words not recalled that is being recorded. This test is a key measure of episodic memory.

- Orientation (0 to 8). The sign of the z-score for this component will be reversed when deriving the Cognitive Composite score as the recorded score for this test is the number of items answered incorrectly. This measure is an index of the study participant's episodic memory and a single item of semantic memory (their name).
- Delayed Word Recall (0 to 10). The sign of the z-score for this component will be reversed when deriving the Cognitive Composite score as it is the total words not recalled that is being recorded.

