- Word Recognition (0 to 24). The sign of the z-score for this component will be reversed when deriving the Cognitive Composite score. This is a further test of episodic memory using a word recognition paradigm of 12 true positive targets and 12 foil items. While the possible score for this measure is 0 to 24, the standard ADAS-Cog score is capped at a maximum worst score of 12.
- Number Cancellation (raw score 0 to 40, subsequently re-scaled to a 5-point scale [0-5]). In this task, the participant is asked to cross off as many target digits as possible in 45 seconds. The score is derived as the number of incorrectly crossed-off items and the number of reminders given subtracted from the number of items correctly crossed off. The resulting score (0-40) is then re-scaled to a 5-point scale (0-5) as described earlier in this section. NTB
  - COWAT This test of working memory and executive function yields a key metric referred to as 'Total number of acceptable words'. This is obtained by calculating how many of the study participant's responses are deemed acceptable according to the scoring rules. The total score for COWAT is the sum of the number of accepted words for each of the 3 tests (three letters). The score range for this test is typically between 0 and 80, though floor performance (a score of 0) is vanishingly rare in mild-to-moderate stage AD participants.
  - CFT This is a further test of working memory and executive function that yields a key metric referred to as 'Total number of acceptable words'. This is obtained by calculating how many of the study participant's responses are deemed acceptable according to the scoring rules. The usual performance range for this test is between 0 and 40.
  - Digit Span This is a brief measure of working memory, especially in the Digits Backwards section. The key metric is 'Total number of trials correct', which is the number of sequences correctly recalled. The range of the test is 0 to 24 and both floor and ceiling effects are rare.
  - Trail Making Test (TMT) A This is essentially a measure of attention, as successful completion relies on quickly and accurately connecting numbered circles in an ascending sequence. The key metric for analysis

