purposes is 'Time taken for completion'. Errors and time taken once again both contribute to performance. However, because errors incur a time penalty, it is not necessary to analyze both metrics. The sign of the z-score for this component will be reversed when deriving the Cognitive Composite score.

- Trail Making Test (TMT) B This is the more complex component of the TMT in which successful completion relies on the study participant accurately connecting the numbered and lettered circles. Study participants are required to alternate between numbers and letters in an ascending sequence. The key metric for analysis purposes is again 'Time taken for completion'. As with TMT A, because errors incur a time penalty, it is not necessary to factor in errors for analysis purposes. The sign of the z-score for this component will be reversed when deriving the Cognitive Composite score.
- The Memory composite score will be a composite z-score average similar to the Cognitive Composite score but will only be derived using the average of the ADAS-Cog Word Recall, Orientation, Delayed Word Recall, and Word Recognition items. If a participant is missing any of the four items at a timepoint, this composite score will not be derived.
- The Attention composite score will be a composite z-score average derived using the average of the Number Cancellation and TMT A items. If a participant is missing either of the two items at a timepoint, this composite score will not be derived.
- The Executive function composite score will be a composite z-score average derived using the average of the COWAT, CFT, Digit Span, and TMT B items. If a participant is missing any of the four items at a timepoint, this composite score will not be derived.

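### Number Cancellation is cut into six bands before it is standardised for the Attention and Cognitive composites, which discards information for no stated reason; the cost is modest and falls mainly on Attention

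*SAP*

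**What the plan says.** SAP section 6.1.8 (Derived Variables) scores Number Cancellation in two steps. Step 1 takes targets hit and subtracts errors and reminders, so higher is better. Step 2 converts that count to bands, most of them six points wide, so that higher is worse: "The resulting final number cancellation item score will range from 0 to 5". Negative counts join the worst band: "Number cancellation item scores < 0 will be re-scaled as 5".

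The component list for the Cognitive Composite then takes the banded score: "The resulting score (0-40) is then re-scaled to a 5-point scale (0-5) as described earlier in this section". On weights, the SAP says "The Cognitive Composite score will be set as the mean of the 10 individual z-scores (5 ADAS-COG scores and 5 NTB scores" and "The Attention composite score will be a composite z-score average derived using the average of the Number Cancellation and TMT A items". The Memory and Executive Function composites do not contain the item.

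Every component is centred and scaled by its own baseline mean and SD before averaging. Section 8.1 analyses change in each composite by MMRM with the baseline composite as covariate. Section 8 calls all efficacy analyses exploratory. Section 6.1.3 treats every p-value outside the ADAS-Cog 11 sequence as nominal.

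**The concern.** The 0-5 metric has a clear use in the ADAS-13 total, where 13 items are summed on their own scales. It has no such use in a composite that standardises each component. There, banding only coarsens the measurement. A participant who moves from 18 to 23 scores no change, while one who moves from 23 to 24 scores a full step. The grouping error enters both the baseline covariate and the follow-up value.

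At stake is precision on the Attention composite, half of which is this item. It is a listed efficacy endpoint (SAP 2.2.2), tested by MMRM (8.1), plotted (8) and correlated with biomarkers (8.9). Grouping error weakens the treatment contrast and those correlations alike.

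**Working it through.** **1. The plan's own power figure.** The only efficacy power in the documents is 81% for ADAS-Cog 11, combined active versus placebo (SAP 3.2): 48 per group, difference 3.0, SD 5.4, 15% dropout.
- Evaluable: 48 × 0.85 = 40.8 on placebo and 81.6 on active.
- SE = 5.4 × √(1/40.8 + 1/81.6) = 1.035, and 3.0/1.035 = 2.897.
- Power = Φ(2.897 − 1.960) = 82.6%, within 2 points of the stated 81%.

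No power is stated for any composite. I take 81% as the starting power for the full-score composite. That is an assumption.

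**2. Size of the grouping error.** A band six points wide adds variance of about 6²/12 = 3 raw points squared. As a share of the banded variance, 3/(SD² + 3), this is 16% at SD 4, 8% at SD 6 and 4.5% at SD 8. These SDs are assumed.

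**3. Effect on the Attention composite.** Let ρ be the visit-to-visit correlation, r the correlation between Number Cancellation and TMT A, and d an equal standardised benefit on both. Let λ = SD²/(SD² + 3) and s = √λ. Both items point the same way. For the sum of the two items:
- Full score: variance V = 2 + 2r; covariance between visits C = ρV; effect 2d.
- Banded: V = 2 + 2rs; C = ρ(1 + λ + 2rs); effect (1 + s)d.
- Residual variance after baseline adjustment: V − C²/V.

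With SD 6, ρ = 0.75, r = 0.3:
- Full: V = 2.600, C = 1.950, residual 1.1375; effect/SD = 2d/1.0665 = 1.875d.
- Banded: λ = 0.923, s = 0.961, V = 2.576, C = 1.875, residual 1.212; effect/SD = 1.961d/1.101 = 1.781d.
- Ratio 1.781/1.875 = 0.950.
- At 81% power the standardised effect is 1.960 + 0.878 = 2.838. Then 2.838 × 0.950 = 2.695, and Φ(2.695 − 1.960) = 76.9%, a loss of about 4 points.

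**4. Range.** The formula, beside a simulation that applies the actual bands (edges taken as inclusive, a score of 30 placed in band 0, raw mean 18 or 22 in the rows shown):

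| Raw SD | ρ | r | Loss, formula | Loss, simulation |
|---|---|---|---|---|
| 8 | 0.60 | 0.5 | 1.2 | 1.5 (mean 18) |
| 6 | 0.70 | 0.3 | 3.4 | – |
| 6 | 0.75 | 0.3 | 4.1 | 3.9 (mean 18), 4.5 (mean 22) |
| 6 | 0.80 | 0.3 | 5.2 | – |
| 4 | 0.85 | 0.3 | 14.1 | 13.6 (mean 22) |

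Losses are in percentage points from 81%. The simulation grid (SD 4-8, ρ 0.6-0.85, r 0.3-0.5, mean 15-22) runs from 1.5 to 13.6.

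If only TMT A responds (mean 18, ρ = 0.75, r = 0.3), the simulated loss is 1.6 to 4.3 points over SD 4-8. If only Number Cancellation responds, it is 4.6 to 12.2.

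**5. Other composites.** As one item of ten in the Cognitive Composite, the same simulation gives a loss of 0.1 to 1.0 point. Memory and Executive Function: zero.

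**The case against.** The banded item is the same score that enters the ADAS-13 total, so the composite and the scale stay consistent. Banding also limits the pull of extreme and negative counts, which the SAP foresees. The primary objective is safety, and the primary exploratory analysis is ADAS-Cog 11, which excludes this item. The size of the loss rests on assumed SDs, correlations and starting power: an effect-size ratio of 0.92 costs about 7 points at 81% power but only about 4 at 30% or 95%.

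Most of this stands. Consistency with ADAS-13 is a real, if small, benefit, although the SAP does not claim it. Extremes could be handled by flooring at 0, and TMT A enters as completion time with no banding. The exploratory status limits the consequence but does not supply a reason to discard collected data.

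A reader might infer more than the documents support:
- **That all the z-score composites suffer.** Two of the four contain the item, and only Attention loses materially.
- **That a definite amount of power is lost.** No SD or correlation for the item is given, so only a range can be stated.
- **That a treatment test on the item itself is weakened.** None is planned: section 8.4 models NTB components, Number Cancellation belongs to ADAS-Cog, and section 8.7 is descriptive.
- **That the plan does the opposite for Word Recognition.** The SAP says "While the possible score for this measure is 0 to 24, the standard ADAS-Cog score is capped at a maximum worst score of 12". It lists the range as 0 to 24 but does not settle which score enters the composite.
- **That the figures hold under any sign.** They assume Number Cancellation is aligned with TMT A. The SAP reverses TMT A for the Cognitive Composite and states no reversal for the banded, higher-is-worse item. With TMT A reversed and this item not, equal benefits on the two would largely cancel.

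**Conclusion.** The point holds as a minor, low-cost improvement. The SAP bands the item before standardising it, standardising makes the bands unnecessary in the composites, and no reason is given. The loss appears in every setting examined. Under the stated assumptions it is roughly 1.5 to 14 points of power for the Attention composite, about 3 to 5 at SD 6 and correlation 0.70 to 0.80, and at most about 1 point for the Cognitive Composite. It biases no analysis on which the trial's main conclusions rest.

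**What to change.** In SAP 6.1.8, compute the Number Cancellation z-score for the Attention and Cognitive composites from the Step 1 score, with no sign reversal, floored at 0 if negative counts are a concern. Keep the Step 2 score for the ADAS-13 total only. In the same sentence, say that the TMT A reversal, written for the Cognitive Composite, also applies in the Attention composite. The two Attention items then point the same way, which closes the gap left by the unstated reversal of the banded item.

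The cost is one sentence and one line of code. Step 1 is already part of the re-derivation in the analysis dataset, and no new data are needed. ADAS-13 and ADAS-Cog 11 are unchanged. The small downside is that the composite item no longer matches the ADAS-13 item score. If the sponsor prefers the banded score, the SAP should give the reason and state the sign reversal. Either change should be made before unblinding.

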#### 6.1.9. Data Adjustments/Handling/Conventions

All collected data will be presented in listings. Data not subject to analysis according to this plan will not appear in any tables or graphs but will be included only in the data listings.

All P-values will be displayed in four decimals and rounded using standard scientific notation (e.g., 0.XXXX). If a P-value less than 0.0001 occurs, it will be shown in tables as < 0.0001. If a P-value greater than 0.9999 occurs, it will be shown in tables as > 0.9999.

Adverse events and medical history will be coded using the latest version of the Medical Dictionary for Regulatory Activities (MedDRA) thesaurus available at the time of database lock.

Prior and concomitant medications will be coded using the latest version of World Health Organization - Drug Dictionary Enhanced (WHO-DDE) available at the time of database lock.

A treatment-related AE is any AE with a relationship to the study drug of probable or possible.

If it is necessary to calculate a participant's age from the (partial or complete) date of birth

(DOB) and the date of the Baseline Visit, the floor function will be used to ensure the participant has an integer age.

If partial AE dates or partial medication dates occur, the convention for replacing missing dates for the purposes of calculating derived variables is as follows:

For partial AE and medication start dates:

- If the year is unknown, then do not impute the date but instead assign a missing value.
- If the year is known, but the month or month and day is unknown, then:
  - o If the year matches the year of first application date and the end date (if present) is after first dose date, or AE/medication is ongoing, then impute as the month and day of the first application date. If this produces a date after the AE/medication end date, assign 01 January.
  - o Otherwise, assign 01 January.
- If the year and month are known, but the day is unknown, then:
  - o If the month and year match the month and year of the first dose date, then impute as the day of the first dose date. If this produces a date after the AE/medication end date, assign 01.
  - o Otherwise, assign 01.

For partial AE and medication end dates:

- If the year is unknown, then do not impute the date but assign as missing value.
- If the year is known but the month or month and day is unknown, then:
  - o If the year matches the year of the last date of the study (date of last contact if participant is lost to follow-up; date of completion or early termination otherwise), then impute as the month and day of the last date of the study.
  - o Otherwise, assign 31 December.
- If the year and month are known, but day is unknown, then:
  - o If the month and year match the month and year of the last date of the study, then impute as the day of the last date of the study.
  - Otherwise, assign the last day of the month.

In general, for quantitative laboratory values reported as '<X' or ' $\le$ X', the lower limit of quantitation (LLOQ) will be used for analysis (i.e., the value of X will be used in the analysis for lab values reported as '<X' or ' $\le$ X'). Similarly, for quantitative laboratory values reported as '>X' or ' $\ge$ X', the upper limit of quantitation (ULOQ) will be used for analysis (i.e., the value of X will be used in the analysis for lab values reported as '>X' or ' $\ge$ X').

For analysis purposes, repeat laboratory test results will not be used unless the original laboratory value is missing or indicated as invalid, in which case the first non-missing repeated laboratory value will be used for data analysis.

Data missing in the exploratory analysis of phospho-tau proteins will be handled according to the SAP provided by Proteome Sciences.

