7.2.1 Safety Stopping Rules

Dosing may be terminated by the Sponsor at the recommendation of the DSMB (Data Safety and Monitoring Board) based on safety and tolerability data, or at the discretion of the Sponsor; as a result, there are no study-specific stopping rules defined in this protocol.

The occurrence of any one of the following events will result in a review of study safety information to date by the Sponsor and DSMB.

- Two occurrences of the same or similar serious adverse event (SAE) assessed as
 probably or possibly related to dosing with investigational product.
- Two or more different participants with the same or similar severe AE assessed as
 probably or possibly related to dosing with the investigational product.

 Four or more participants with the same or similar moderate AE which is possibly or probably related to dosing with investigational product.

Under these circumstances, the Sponsor and DSMB will review the available safety data and recommend whether dosing should continue, or if study drug administration should be terminated, or if additional monitoring procedures or safety precautions need to be employed. Selective unblinding of the participants in the study may be performed by the Sponsor and DSMB to determine if the SAEs/AEs are isolated to a single dose group or if they occurred in placebo participants.

The study or a dose group may also be terminated if the Sponsor and DSMB determine that any adverse event(s) are occurring that are intolerable or pose a medically unacceptable safety risk.

For individual participants:

Any participant who develops the following liver function test (LFT) laboratory abnormalities will not receive any additional doses and will be monitored until resolution of the AE or the return of laboratory abnormality to the acceptable screening value(s).

- Elevated ALT or AST greater than 5 X Upper Limits of Normal (ULN)
- elevated ALT or AST greater than 3 X ULN in combination with total bilirubin > 2 X ULN or INR > 1.5 X ULN
- ALT or AST > 3 X ULN with the appearance of fatigue, nausea, vomiting, right upper quadrant pain or tenderness, fever, rash, and/or eosinophilia (>5%)

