Serial monitoring of ALT/AST/bilirubin and INR will be performed, initially with repeat values within 4 days of discontinuation of study drug. If LFTs are still elevated 4 days post-study drug interruption, participants should have LFTs checked again 4 days later (+/- 1 day). The site investigator and Medical Monitor should agree to a plan for further LFT monitoring depending on whether the LFTs are still increasing or trending towards normal. Repeat testing should be carried out until LFTs have normalized. The LFTs in this instance can also be run locally for more rapid turnaround.

In the event a reversible etiology is found to explain the elevated liver enzymes (such as a common bile duct stone), drug may be restarted following normalization of LFTs, and after discussion between the Medical Monitor and site PI.

Study drug will be temporarily discontinued if a participant does not achieve the aforementioned levels of elevated transaminases but has an elevation of ALT or AST >3 X

ULN. These participants will have their liver function retested within 4 days after their last dose of study drug. If transaminases are still elevated 4 days post-study drug interruption, participants will have LFTs checked again 4 days later (+/- 1 day), and the site PI and Medical Monitor will agree to a plan for further monitoring of the findings. The LFTs in this instance can also be run locally for more rapid turnaround.

LFTs do not need to be intensively monitored when ALT and AST are ≤ 3 X ULN with no elevation of bilirubin, however the investigator and the Medical Monitor will formulate a plan for serial testing of LFTs. Cessation of dosing is not required in this circumstance but may be temporarily interrupted at the discretion of the investigator.

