#### 9.2. Clinical Laboratory Evaluations

#### 9.2.1. Protocol-Required Safety Laboratory Tests

Hematology testing will include erythrocyte (red blood cell count), erythrocyte mean corpuscular hemoglobin concentration (MCHC), erythrocyte mean corpuscular volume (MCV), hematocrit, hemoglobin, and absolute counts of leukocytes, lymphocytes, monocytes, neutrophils, basophils, eosinophils, and platelets. Coagulation testing (prothrombin time [PT/INR]) will be performed at screening and Day 154 only.

Serum chemistry analyses will include glucose, calcium, albumin, protein, sodium, potassium, bicarbonate, chloride, magnesium, fractional calcium excretion, blood urea nitrogen (BUN), creatinine, creatine kinase, alkaline phosphatase, Alanine Aminotransferase (ALT), Aspartate Aminotransferase (AST), bilirubin, lipase, lactate dehydrogenase (LDH), and phosphate.

Urinalysis will include osmolality, creatinine, calcium, erythrocytes, leukocytes, sodium, specific

gravity, pH, specimen appearance (turbidity), color, protein, glucose, ketones, bilirubin, hemoglobin, urobilinogen, nitrite, and microscopic particles. Trace protein will be considered positive. Urine samples that did not have preservative added prior to lab analysis will be listed only.

All summaries of laboratory values from local and central lab will be presented using SI units. Observed hematology, chemistry, and urinalysis values and changes from baseline at each visit will be summarized by treatment received. Shifts from baseline regarding low/normal/high values will also be summarized by treatment received.

Shift tables summarizing the most extreme post-baseline shift for each participant within each lab parameter will be presented, with low and high results considered more extreme than normal. If a participant has both a low and high post-baseline result within a parameter, they will be counted within both the low and high rows.

The incidence of post-baseline ALT values  $\ge 3xULN$ , AST values  $\ge 3xULN$ , and AST or ALT values  $\ge 3xULN$  will be summarized.

All chemistry, hematology, and urinalysis data will be listed.

Screening laboratory tests such as viral serology, thyroid stimulating hormone, follicle-stimulating hormone, HbA1c, Folate, B12, and urine pregnancy test results will be listed only.

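### Follow-up liver tests may be kept out of the worst-value tables, and no planned table separates the protocol's own liver stopping criteria

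*SAP*

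**What the plan says.** **Repeat rule.** SAP 6.1.9 states that, for analysis, "repeat laboratory test results will not be used unless the original laboratory value is missing or indicated as invalid". When the original is missing or invalid, the first available repeat replaces it. The rule does not define a repeat and names no table to which it does not apply. The same section says that data not analysed under the plan go into listings only.

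**Planned laboratory tables.** SAP 9.2.1 plans these outputs:

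- By-visit tables of chemistry, hematology and urinalysis, both as measured and as change since baseline, for each arm.
- Tables of movement between the low, normal and high categories relative to baseline, for each arm.
- Worst-value tables, described thus: "Shift tables summarizing the most extreme post-baseline shift for each participant within each lab parameter will be presented".
- One threshold summary, beginning "The incidence of post-baseline ALT values", which covers ALT, AST, and either enzyme, each at or above 3xULN.

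PT/INR is named as a test, but the sentence on summaries leaves coagulation out.

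**Protocol liver rules.** Under Protocol 7.2.1 a participant gets no further doses at ALT or AST >5xULN, at >3xULN "in combination with total bilirubin > 2 X ULN or INR > 1.5 X ULN", or at >3xULN with listed symptoms or eosinophilia. After such a stop, "Serial monitoring of ALT/AST/bilirubin and INR will be performed, initially with repeat values within 4 days of discontinuation of study drug", and repeat testing goes on until values are normal. A rise above 3xULN without the other features leads to a temporary stop and a retest within 4 days. In both cases, values still raised are checked again 4 days later (+/- 1 day). At or below 3xULN with no bilirubin elevation, the investigator and Medical Monitor agree a plan for serial testing, and dosing need not stop.

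**The concern.** Keeping the first valid result is sensible for by-visit means, because it stops participants who are retested from being weighted by their retests. It suits a worst-value table poorly, since such a table is meant to report the highest value reached, and a liver signal may develop over the days after it is first seen.

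Safety and tolerability are the primary objective, and the liver rules are the only individual-participant laboratory stopping rules in Protocol 7.2.1. Protocol 4.3 says that later studies will monitor liver enzymes closely, to tell sporadic findings from drug-related ones. It also reports one participant with ALT at 4.7xULN in the 28-day study in Alzheimer's disease. That was at 560 mg, above both doses tested here, and it resolved after the drug was stopped. A reader of the final report will want to know, by arm, how many participants met each protocol liver criterion. The planned tables cannot answer that.

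**Working it through.** The plan gives no figure for this point, so most of the check sets rules against outputs.

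**1. Does the repeat rule reach the follow-up tests?** SAP 6.1.9 speaks of repeat results. Protocol 7.2.1 uses the same word for the serial tests after a stop. Nothing in SAP 9.2.1 exempts the most-extreme shift tables or the >=3xULN incidence. Exclusion is therefore the natural reading for follow-up above 3xULN. It is less clear at or below 3xULN, where the protocol speaks of serial testing.

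**2. Would scheduled visits pick up the same values?** Assume that drug is stopped on the day of the abnormal visit.

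- Latest second retest: 4 + 4 + 1 = 9 days after that visit.
- Shortest gap between scheduled clinic visits from Day 28 on (Part C: from Day 14 on): 14 days.
- Next window opens at 14 - 2 = 12 days, or 12 - 2 = 10 days if the first visit was itself 2 days late.
- 9 < 10, so neither retest falls in another scheduled window.

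Earlier visits are closer together and can overlap: in Parts A and B, Day 21 + 9 = Day 30, inside the Day 28 window (26 to 30). A delay between sampling and stopping would move the retests later by the same number of days. Subject to that, follow-up values are normally unscheduled, and SAP 6.1.6 builds summary tables on the nominal visit.

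**3. Which protocol criteria can be read from the planned tables?**

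| Protocol 7.2.1 criterion | Planned by-arm laboratory output |
|---|---|
| ALT or AST >5xULN | No category; falls in the >=3xULN row |
| >3xULN with bilirubin >2xULN | No joint table; enzyme in the >=3xULN row, bilirubin in low/normal/high shifts |
| >3xULN with INR >1.5xULN | No joint table; INR in no summary |
| >3xULN with symptoms or eosinophilia | No joint table; parts appear separately in adverse event and hematology tables |
| >3xULN alone (temporary stop) | Covered by the >=3xULN row |

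All of these imply a value above 3xULN. A participant whose triggering value is analysed is therefore counted once at >=3xULN, but the row cannot say which criterion was met.

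For INR, SAP 9.2.1 gives screening and Day 154 as the only test days. Protocol 13.1.4 adds Day 70 when a Day 98 lumbar puncture is planned. The INR criterion will mostly rest on follow-up samples.

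**4. Illustration (invented values).** A participant has ALT 3.5xULN with normal bilirubin at a visit, then ALT 6xULN and bilirubin 2.5xULN on the retest. If the retest is excluded, the tables show one count at >=3xULN and no bilirubin shift, the same as for someone whose ALT fell back to normal. If the retest is included, the bilirubin shift appears, but still no >5xULN count and no joint event.

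**5. Size.** One missed participant is 1/48 = 2.1 percentage points of an arm, or 1/96 = 1.0 point of the pooled CT1812 group. The protocol's own yardstick is the chance of at least one event among 48 at a 5% rate: 1 - 0.95^48 = 0.915, matching its 91%. For rarer events (assumed rates) the chance is 1 - 0.98^48 = 0.621 at 2% and 1 - 0.99^48 = 0.383 at 1%, with expected counts of 48 x 0.02 = 0.96 and 48 x 0.01 = 0.48. A severe combined event would probably show as one case or none, so one omission could remove the whole observation.

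**The case against.** The strongest reply is that the SAP rule may concern only redraws of a single scheduled test. Its wording, in which a repeat stands in for a missing or invalid original, fits that use, and a sample taken days later is no substitute for an invalid one. SAP 9.2.1 also says "All summaries of laboratory values from local and central lab will be presented using SI units", and Protocol 7.2.1 allows follow-up liver tests to be run locally, which hints that follow-up values may be included. This stands as far as it goes: exclusion is the likelier reading, not a certain one. It does not remove the need to say which values feed the worst-value tables.

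A reader might infer three stronger things that the documents do not support:

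- *That repeat results are thrown away.* All collected data are listed, and a repeat replaces a missing or invalid original.
- *That >=3xULN is the only liver table.* By-visit summaries, low/normal/high shifts and most-extreme shifts are planned for chemistry, which includes ALT, AST and bilirubin. What is true is that >=3xULN is the only summary in multiples of ULN.
- *That the excluded values are the ones on which drug is stopped, so that stops vanish from the safety tables.* Most follow-up values come after a stop. The exceptions are a retest after a temporary stop, or a serial test at or below 3xULN, that is the first to meet a criterion.

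Other outputs also capture part of this. Protocol 13.2.1 makes a clinically significant laboratory abnormality an adverse event, and SAP 9.1.1 tabulates by arm those leading to treatment discontinuation. That helps with lasting stops, but it depends on the investigator's judgement. The action codes in Protocol 13.2.2.4 (none, reduced, discontinued) have no entry for an interruption, so a temporary stop need not appear there. Listings give no by-arm incidence.

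**Conclusion.** The point holds in two parts of different certainty.

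The firm part is that no planned table separates >5xULN, none shows the bilirubin, INR or symptom/eosinophilia combinations in Protocol 7.2.1, and INR is not summarised. This does not depend on how a repeat is defined.

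The likely part is that follow-up liver tests do not feed the most-extreme shift tables or the >=3xULN incidence. It rests on reading the SAP's repeat in the sense in which the protocol uses the word. Participants whose first analysed value already reaches 3xULN are still counted at that level. What could be lost from the by-arm laboratory tables is a first crossing of 3xULN on a follow-up test, or a bilirubin shift that appears only on follow-up.

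Each missed participant is worth 2.1 percentage points of a planned arm of 48. The documents give no basis for estimating how many there would be, and the number may be zero. With full listings, discontinuation tables and quarterly DSMB review, this should be fixed, but it does not invalidate the safety analysis. Confidence is moderate.

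**What to change.** **SAP 6.1.9.** Define a repeat, and limit the exclusion to by-visit descriptive summaries. State that most-extreme shift tables and threshold incidences use all post-baseline values: scheduled, unscheduled, repeat, central and local.

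**SAP 9.2.1.** Add one table of participants by arm, and for pooled CT1812, meeting each existing criterion in Protocol 7.2.1:

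- ALT or AST >5xULN;
- ALT or AST >3xULN with total bilirubin >2xULN;
- ALT or AST >3xULN with INR >1.5xULN;
- ALT or AST >3xULN with the listed symptoms or eosinophilia.

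State how close in time the paired results must be, and add a summary of INR.

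**Cost.** Some SAP wording and one small table. The protocol already requires the liver and INR follow-up. The last criterion needs laboratory records matched to adverse events by date, and the eosinophil percentage derived from the absolute and leukocyte counts. Worst-value counts may look slightly less favourable. By-visit tables do not change, and no clinical threshold or stopping rule is altered. The change should be made before unblinding for the final analysis; if made later, it should be labelled post hoc, as the SAP overview requires.
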